The goal of the proposed intervention, called LEAF (Life Enhancing Activities for Family Caregivers) is to reduce burden and increase well-being in Alzheimer’s Disease caregivers through the practice of positive emotion skills. We will evaluate two methods of online delivery of LEAF: facilitated and self-guided and compare them to an emotion-reporting waitlist control condition. If effective, the LEAF program can be disseminated to Alzheimer’s caregivers nation-wide.

3.0 Inclusion and Exclusion Criteria:

Inclusion criteria:

- Age 18 and over
- Identifies as the primary family caregiver of a person with Alzheimer’s Disease (AD)
- Speaks and reads English
- Has access to high speed internet connection at home or in a location where they can speak privately with a facilitator (e.g. a library)

4.0 Sample Size:

We will recruit a total of 500 participants nationwide into the LEAF 2.0 randomized controlled trial. Once participants complete the online consent and baseline questionnaire, they will be randomized 2:2:1 to Facilitated LEAF (N = 200), Self-guided LEAF (N = 200) or emotion reporting waitlist control (N = 100). The waitlist control group will crossover during the study to receive either the Facilitated LEAF (N = 50) or the Self-guided LEAF (N = 50).

5.0 Research Locations:

Research will be based at Northwestern University's (NU) Feinberg School of Medicine through the Department of Medical Social Sciences (MSS) as the lead research site. NU holds the IRB of record. The research will involve Bright Outcome (<https://www.brightoutcome.com/>), a company experienced in designing online platforms for patient reported outcomes research. Bright Outcome has a proven track record of collaboration and delivery of technology products/services to investigators at the Feinberg School of Medicine.

6.0 Multiple sites:

Northwestern University is the lead (primary) research site for the LEAF 2.0 Study. The University of California San Francisco (UCSF) is the secondary research site for the LEAF 2.0 Study. The Principal Investigator ([name]), co-Investigators ([name] and [name]), the NU Project Director ([name]) are at NU, in addition to the several team members who are doctoral students mentored by [name], and other research assistants on the project. Only IRB-approved staff will have contact with participants.

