- If a participant consents “Yes,” they will automatically continue on to complete the online baseline assessment (T1).
- If an individual does not respond to the consent form, our study team will follow-up with a reminder up to 3 times by phone or email (based on information provided on the screener).
- If an individual responds “No” and declines to participate, they will see a message thanking them for their time, and answer a brief (optional) question about why they declined.

Consenting individuals will continue to take the baseline assessment (T1) which takes up to 1 hour. Once the baseline assessment is complete, participants will be randomized to either the Facilitated LEAF “Video Session” Group (N=200), Self-guided LEAF “Online Lessons” Group (N=200), or an emotion reporting waitlist control. Both the “Online Lessons” and “Video Sessions” consists of 6 modules for the intervention; one-module unlocked per week over 6 weeks, but participants will have an 8-week period to complete the 6-module intervention. The emotion reporting control group reports their daily emotions for 8-weeks (equivalent to the 8-week intervention period), and then crosses over to receive the intervention at time point 4 (T4) as either the “Video Sessions” (N=50) or “Online Lessons” (N=50), after a waiting period of 7 months. Home practice exercises and the daily emotion check-ins will be done over the internet on the Bright Outcome platform for all research arms (N=500). The intervention content, emotion reporting forms, and assessment questionnaires are all mobile-enabled so can be completed on desktop, laptop, tablet, or smartphone.

Randomization:

Condition 1: one-on-one video sessions with a facilitator

Condition 2: self-guided online lessons

Condition 3: emotion reporting condition that will get either the one-on-one video sessions or self-guided online lessons later

Mailing and Receiving a Tablet

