During the screening call, study staff will assess whether participant has a device at home with which they can access study activities (computer, tablet, or smartphone). After a participant has been randomized, the PD will mail a tablet to participants who do not have a device they can use to access study activities, and are receiving the LEAF 2.0 intervention right away e.g. those randomized to the “Videos Sessions” **Condition 1** or “Online Lessons” **Condition 2** (NOT in the emotional reporting control group). Emotion-reporting participants (**Condition 3**) who need a study tablet will receive the tablet at T4 when they

complete the waitlist portion of the study and just prior to the beginning of the intervention. The PD will mail and track the delivery of a tablet to the participants who opt in to receiving one.

6 Sessions over 8 Weeks: 60 min/session

Facilitator-Guided Intervention “Video Sessions”

Since the intervention is delivered online, caregivers will participate in a place of their choosing that offers privacy and comfort. Facilitators will participate in a private room in their work setting. The sessions will take place over approximately 8 weeks (6 weekly modules and online home practice with 2 weeks of “catch-up”). Sessions will be conducted on an encrypted internet connection and all sessions will be video-recorded on Zoom for both quality assurance and intervention evaluation. They will also complete daily stress and emotion questions included in the control condition. Between training sessions, participants in the facilitator-guided sessions will complete home exercises and write daily experiences on the Bright Outcome online platform. Bright Outcome data we are collecting also include number of log-ins, progress in the course, completed home exercises, number of audio plays on the meditation file, content page access, etc. These data will be securely stored on Northwestern servers, accessible only to IRB-approved study staff.

6 Sessions over 8 weeks: approx. 30 minutes/online module

Week Self-Guided Intervention “Online Lessons”

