Simple group comparisons for single time points or pre-post comparisons between the facilitated (n=200) and self-guided (n=200) groups will have 80% power to detect effect

sizes of $d=.28$ ($R^2=.019$), below the observed effect sizes for positive emotion, negative emotion, stress, depression, and anxiety in our previous LEAF trial. Comparisons between the wait-list control group ($n=100$) and the LEAF interventions individually ($n=200$) or taken together ($n=400$) will have 80% power to detect effect sizes of $d=.34$ ($R^2=.029$) and $d=.31$ ($R^2=.024$), respectively.

Our design of seven time points and 500 individuals exceed established minimums for detecting predictors of individual differences¹⁰⁸ and for detecting associations between parallel growth processes.¹⁰⁹ Power for these models was estimated by Monte Carlo simulation to account for our longitudinal experimental design. Effects of observed predictors (i.e., LEAF group, Aim 1) had 80% power for effects of $d=.27$ ($R^2=.018$). Parallel growth curves showed 80% power for slope correlations of $r=.14$ ($R^2=.019$), and comparable power for indirect effects of ($r=.15$, $R^2=.021$), consistent with previous work on mediational power.¹¹⁰

Missing Data

Although our previous test of LEAF showed high adherence rates and minimal dropout, all longitudinal analyses must plan for missing data. All proposed models will be fit with full information maximum likelihood, which yields unbiased parameter estimation under common missing data mechanisms. Multiple imputation will be used in any cases where covariates predict missingness but would otherwise not be included in proposed models.

9.0 Incomplete Disclosure or Deception:

N/A

10.0 Recruitment Methods:

We plan to recruit participants over the period of 42 months. Recruitment efforts will target the 2 major national organizations servicing patients with dementia and their caregivers: 1) the Alzheimer's Association and 2) the Family Caregiver Alliance: National Center on Caregiving.

We will also use print, radio, and websites at the national and local level of these organizations to access a geographically and age diverse cohort. Subjects will also be recruited from the Northwestern University Alzheimer's Center, the University of California San Francisco Memory and Aging Center, The New Normal, and the NUCATS recruitment tool. We will also recruit on Alzheimer's-related websites that give us permission to post.

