13.0 Audio/Video Recording

The facilitator-guided LEAF sessions will be digitally video- and audio-recorded using a secure, encrypted internet connection on a password-protected platform such as Zoom. Each participant in the facilitator-guided intervention will have approximately 6 audio-recorded sessions (one for each intervention session, 6 total), recorded for quality assurance purposes and to evaluate the intervention. These recordings will be securely stored on Northwestern password-protected servers, accessible only to IRB-approved staff. The videos will be labeled by Study ID.

Fidelity will be assessed qualitatively with a checklist and comments for each component of a session as we have done in LEAF 1.0 and other face-to-face delivery of the intervention. Sessions will be reviewed by the project director to assess adherence to the protocol, delivery, facilitator/participant rapport, and session flow. All sessions of the first three participants (for each facilitator) will be reviewed immediately. This will be followed by regular (weekly, then monthly) reviews of selected sessions thereafter.

14.0 Potential Benefits to Participants:

There is no guaranteed benefit from participating in LEAF 2.0, however participants might enjoy the skills taught in LEAF and continue practicing them beyond the online course e.g. keeping a gratitude journal, completing everyday chores mindfully, or listening to a breath awareness meditation recording. Participants may gain mindfulness skills, regularly capitalize on positive events, or use positive reappraisal to reassess daily stressors. Even after completing the course, participants are encouraged to keep using their favorite skills, whether formally through the website and/or journaling about their experiences, or informally in their everyday lives.

On a broader scale, we predict that the skills taught in LEAF 2.0 may help family caregivers of dementia patients increase their positive affect and lower depression, anxiety, and perceived stress. We will explore the effects of this intervention on caregiving burden, caregiving efficacy, positive aspects of caregiving, quality of care, and AD patient quality of life. We will assess whether these effects on outcomes are mediated by improvements in positive emotion.

15.0 Risks to Participants:

Minimal Risk; Possible discomfort while interacting with the LEAF platform

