Official title: Randomized Trial of a Technology-based Positive Emotion Intervention for Informal Caregivers of Individuals With Alzheimer's Disease

Brief title: Life Enhancing Activities for Family Caregivers (LEAF 2.0)

NCT#: NCT03610698

Date: 10/20/2025

Demographic characteristics, including age, gender, race, ethnicity, income, education, and residence were summarized for the sample as a whole, and by intervention group (Facilitated Intervention, Self-Guided Intervention, and combined Control). Differences between groups were calculated using one-way ANOVA for continuous variables and Chi-squared tests for categorical variables; Fisher's exact tests were used when required by the distribution. Baseline scores for each outcome were compared across the three groups using ANOVA and Kruskal-Wallis tests, depending on the distribution of the data.

Change over time and differences within- and between- intervention groups were assessed using mixed effects linear regression models. Time (baseline, post-intervention, follow-up 1 and follow-up 2) was treated categorically to allow for slope estimates to differ between consecutive timepoints. Models included a random effect for intercept and time. From these models, within-group and between-group differences across intervention groups (Facilitated, Self-Guided, and Control) were estimated between baseline and each follow-up time point (post, FU1, and FU2) using least square means estimates. Effect sizes were calculated to compare change over time across intervention groups.

Lastly, we calculated the number of sessions/weeks completed for each participant during their intervention period to assess how the number of weeks completed moderate the effect of intervention on change in each outcome. We used mixed effects linear regression models including time, intervention group, and usage (none, some, or all sessions) to estimate the change from baseline to each follow-up (post, FU1, and FU2) in both intervention groups, and test for significant change both within and across intervention groups (facilitated, self-guided).

All analyses were performed using SAS v. 9.4; p-values were considered significant at $p < 0.05$.

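### The SAP model has no facilitator term, so if outcomes in the facilitated arm cluster by facilitator, the standard errors for that arm's contrasts will be too small, by an amount the documents do not allow one to calculate

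*SAP*

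**What the plan says.** The SAP's second paragraph analyses change with mixed linear models in which time is categorical. On random structure it says only: "Models included a random effect for intercept and time". The level is not named; I read it as the participant. Between-group and within-group changes from baseline to each of three follow-ups come from these models. The usage model in the third paragraph lists time, group and usage. Neither model has a facilitator term, and neither document mentions an ICC, a design effect or cluster-robust standard errors.

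On delivery, protocol section 8.0 lists "Condition 1: one-on-one video sessions with a facilitator". Section 13.0 adds: "Each participant in the facilitator-guided intervention will have approximately 6 audio-recorded sessions". The same section shows that facilitators are shared: "All sessions of the first three participants (for each facilitator) will be reviewed immediately".

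Section 4.0 plans 200 facilitated, 200 self-guided and 100 control participants. The Power text gives detectable effects at 80% power of d = .28 for facilitated v self-guided. For control against either LEAF arm, and against both together, it gives .34 and .31.

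**The concern.** People treated by the same facilitator may have more similar outcomes than people treated by different ones. Section 13.0 itself has sessions reviewed for adherence to the protocol, delivery and rapport, all of which can differ between facilitators. Controls only report emotions until they cross over at T4, and the self-guided arm is mostly described as online lessons. On that reading the clustering sits in one arm: a partially nested design. A model with participant-level random effects only treats the facilitated participants as independent of each other.

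Two central comparisons are exposed. Facilitated v control is part of Aim 1. Facilitated v self-guided is the first comparison in the Power text, and it bears on whether a human facilitator adds anything. A standard error that is too small makes p-values too low and intervals too narrow for both.

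**Working it through.** **Inputs from the documents.** Arm sizes 200, 200 and 100 (section 4.0); alpha .05 (SAP; two-sided testing reproduces the power figures, one-sided gives about 87% power); more than one facilitator, each expected to see at least three participants (section 13.0).

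**Assumed, because the documents are silent.** Number of facilitators k = 4, 8 or 20, with equal caseloads m = 200/k and one facilitator per participant; ICC of the change score = 0, .02 or .05; no clustering in the other two arms.

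**Step 1: the plan's own figures.** With independent participants, detectable d = (1.960 + 0.842) × √(1/n₁ + 1/n₂):

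- 200 v 200: 2.802 × 0.1000 = 0.280 (stated .28)
- 200 v 100: 2.802 × 0.1225 = 0.343 (stated .34)
- 400 v 100: 2.802 × 0.1118 = 0.313 (stated .31)

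These reproduce, so the pairwise figures make no allowance for clustering. The Monte Carlo figure of d = .27 cannot be checked, because its inputs are not given.

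**Step 2: design effect in the facilitated arm.** DE = 1 + (m − 1) × ICC. For k = 4, ICC .05: 1 + 49 × .05 = 3.45. For k = 20, ICC .02: 1 + 9 × .02 = 1.18.

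**Step 3: true SE over model SE.** Ratio = √[(DE/200 + 1/n₂) / (1/200 + 1/n₂)], where n₂ is the size of the comparison arm. For k = 4, ICC .05:

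- v self-guided: √[(3.45 + 1)/2] = 1.49
- v control: √[(3.45 + 2)/3] = 1.35

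For change within the facilitated arm the ratio is √DE.

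**Step 4: actual type I error of the unadjusted test.** 2 × [1 − Φ(1.96/ratio)].

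| k | ICC | DE | v self-guided: SE ratio | type I | v control: SE ratio | type I | within-arm SE ratio |
|---|---|---|---|---|---|---|---|
| any | 0 | 1.00 | 1.00 | 5.0% | 1.00 | 5.0% | 1.00 |
| 20 | .02 | 1.18 | 1.04 | 6.0% | 1.03 | 5.7% | 1.09 |
| 8 | .02 | 1.48 | 1.11 | 7.8% | 1.08 | 6.9% | 1.22 |
| 4 | .02 | 1.98 | 1.22 | 10.8% | 1.15 | 8.9% | 1.41 |
| 20 | .05 | 1.45 | 1.11 | 7.7% | 1.07 | 6.8% | 1.20 |
| 8 | .05 | 2.20 | 1.26 | 12.1% | 1.18 | 9.8% | 1.48 |
| 4 | .05 | 3.45 | 1.49 | 18.9% | 1.35 | 14.6% | 1.86 |

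A simulation of change scores (20,000 runs per setting, ICC .02 and .05) gave 6.2% to 18.3% for facilitated v self-guided and 5.6% to 14.3% for facilitated v control. At ICC 0 it gave 5.0% to 5.3%.

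A ratio of 1.49 means that the model SE is about 33% too small (1 − 1/1.49). If both LEAF arms are pooled against control, the ratio at ICC .05 is only 1.02 to 1.12.

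**Step 5: what a correct analysis costs at the worst corner (k = 4, ICC .05, v self-guided).** The two variance parts are 3.45/200 = 0.01725 and 1/200 = 0.005. Satterthwaite df = (0.02225)² / (0.01725²/3 + 0.005²/199) ≈ 5, so t ≈ 2.57. Interval width relative to the unadjusted model is 1.49 × 2.57/1.96 ≈ 1.96.

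**The case against.** A reader might infer that the standard errors of every facilitated-arm contrast are too small as a matter of fact, because a few facilitators each treat many people. The documents do not support that. Section 13.0 shows only that there is more than one facilitator and that each is expected to see at least three participants. Recruitment runs over 42 months and two sites, and nothing caps the pool. At ICC 0 nothing changes, and the 18.9% figure belongs to the most extreme pairing of the assumed values.

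Three further points deserve weight.

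- **Target of inference.** If conclusions were meant only for these facilitators, treating them as fixed need not understate the SE. The SAP does not state its target. However, the protocol aims at nationwide dissemination (section 2.0) and describes delivery by trained lay people (section 15.0). That favours random facilitators without proving it.
- **Few facilitators.** The variance component would then be imprecise and could be estimated as zero. This stands, and is a reason to show both models.
- **Unclustered comparison arm.** This is not secure. One paragraph of section 8.0, on the self-guided version, describes hour-long weekly video sessions booked with a facilitator. The randomization list, the self-guided label and the participant timeline in the same section describe self-guided lessons. Self-guided participants also share a staff-moderated discussion forum. These passages could extend the clustering to a second arm; they do not remove it from the first.

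**Conclusion.** The omission is certain: the SAP has no facilitator term, and facilitators are shared. The consequence is conditional. If post-baseline outcomes cluster by facilitator, and facilitators are regarded as a sample from a wider pool, the SEs for the two pairwise facilitated-arm contrasts and for within-arm change will be too small.

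The size is unknown. Over the assumed grid it runs from nothing, through a 4% larger SE that would hardly matter, to a roughly fourfold type I error. The effect is largest for within-arm change, smaller against self-guided, smaller again against control and slight for the pooled LEAF arms. The documents offer no facilitator count or ICC that would justify ignoring the issue, and a re-fit would help to settle it. It should be corrected, as an inexpensive improvement to central contrasts rather than as proof that the results are wrong.

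**What to change.** 1. Fit a partially nested version of the SAP model. Add a facilitator random effect that acts only on post-baseline visits of facilitated-arm participants, with Kenward-Roger or Satterthwaite degrees of freedom. A facilitator intercept held constant over all visits would not serve, because it largely cancels from change since baseline.
2. Report both facilitated-arm contrasts from this model beside the current one, with the number of facilitators, their caseloads and the estimated ICC.
3. State that no facilitated-arm effect will be claimed if it holds only when clustering is ignored.
4. Reconcile the section 8.0 descriptions of self-guided delivery before treating that arm as unclustered.

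**Cost.** The SAP is dated 10/20/2025 and written in the past tense, so this means a re-fit in SAS, with no new outcome data. It needs a facilitator ID linked to each Study ID. Recordings are labelled by Study ID and early reviews are organised by facilitator, so the link should be recoverable, but the documents do not confirm it. Intervals will generally be wider: hardly so if facilitator variance is near zero, and nearly twice as wide with very few facilitators and a high ICC. With few facilitators the ICC estimate will be imprecise and should be presented as such.

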In the self-guided version of LEAF, the skills will be delivered within 8 weeks (6 weekly, hour-long sessions, scheduled with a facilitator within an 8-week period) via video-conference on a device of their choice. Caregivers can participate from their home computer, smartphone, or a study supplied tablet if they opt to receive one, from a location with wifi. A week will consist of 1-2 days of didactic material and 5-6 days of real-life skills practice and reporting. Participants cannot skip ahead, and can only progress to the next lesson if they have completed the current one, but they can return to old lessons or exercises if they wish to. As part of the daily home practice, intervention participants will be asked to complete the daily stress and emotion questions included in the control condition. Data from participants engaged in the self-guided LEAF skills condition collected from the Bright Outcome platform will be securely stored on Northwestern servers, accessible only to IRB-approved study staff. These data include number of log-ins, completed home exercises, number of skills completed, data from the daily emotion reporting surveys, number of awards earned, discussion posts, etc.

Waitlist/Emotion Reporting Control Condition

In past research we have established that emotion reporting is acceptable as a control condition and that participants perceive it as being beneficial. Participants will be asked to log on to the website daily for 8 weeks, comparable to the 8 week intervention period. They will be prompted to report on positive and negative emotions and stressful events experienced in the past day. Based on past studies, we expect that this reporting will be about 5 minutes per day. Note that participants in the LEAF intervention conditions will also be completing the daily reporting of emotions and stress as part of their home practice. Data from the emotion reporting will also be tracked/exported from the Bright

Outcome platform and securely stored on Northwestern servers, accessible only to IRB-approved staff.

Time Commitment

The estimated time commitment for participating in the LEAF Study is up to 30 hours over 14 months, depending on research condition. Conditions 1 and 2 (who receive the LEAF Skills right away) will spend up to 25.5 hours in the study. Condition 3 (who wait 7 months before receiving the LEAF Skills) will spend up to 30 hours in the study.

Conditions 1 and 2: <24.5 hours

Event	Time Commitment

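### The SAP treats sessions completed, which arise after randomization, as a moderator of the LEAF effect and tests them at 0.05, so shared causes of completion and change could appear as a dose effect.

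*SAP*

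**What the plan says.** The SAP's usage paragraph, its last analysis, builds the exposure from what participants did after assignment: "we calculated the number of sessions/weeks completed for each participant during their intervention period". The stated purpose is "to assess how the number of weeks completed moderate the effect of intervention on change in each outcome". The model is given in one sentence: "We used mixed effects linear regression models including time, intervention group, and usage (none, some, or all sessions) to estimate the change from baseline". It is used to "test for significant change both within and across intervention groups (facilitated, self-guided"). The SAP closes with a general rule that "p-values were considered significant at $p < 0.05".

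The protocol (section 8.0, consent and randomization) fixes the order of events: "Once the baseline assessment is complete, participants will be randomized to either the Facilitated LEAF" or one of the other two arms. Allocation (section 4.0) is as follows: "they will be randomized 2:2:1 to Facilitated LEAF (N = 200), Self-guided LEAF (N = 200) or emotion reporting waitlist control (N = 100"). No session can precede assignment.

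For the usage model the SAP names no covariate, weighting, instrument or principal-stratum method. It does not list control among the groups, and it does not label the result descriptive.

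**The concern.** A moderator is normally a characteristic fixed before treatment, so that arms can be compared within its levels with randomization intact. Sessions completed are not of that kind. They can depend on distress, caregiving load and motivation, all of which may also predict how the outcomes move. The protocol gives one such route: section 17.0 lets participants skip exercises that upset them, and the Aim 1 outcomes include depression, anxiety and perceived stress.

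Completion also means different things in the two arms. One arm books sessions with a facilitator. The other works through lessons that open only after the previous one is done (section 8.0). Caregivers who finish everything in one arm need not resemble those who finish in the other.

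At stake is what may be concluded from this paragraph. A significant usage term could be read as evidence that more sessions work better, and an arm difference conditional on usage as evidence about delivery mode. Self-selection could produce the first on its own, and under further conditions the second. A finer scale for usage would not remove the problem.

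**Working it through.** **Inputs from the documents.** 200 per LEAF arm (protocol 4.0); significance level 0.05 (SAP), taken as two-sided; stated detectable facilitated versus self-guided difference d = .28 at 80% power (protocol 8.0, Power).

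**Assumed inputs, because the documents give none.** Correlation r between latent engagement and standardized outcome change of .1, .2 or .3; completion splits as shown below; complete follow-up unless stated. True effects of dose and of mode are zero throughout.

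**1. The plan's own figure.** For 200 v 200 at d = .28: z = .28/√(1/200 + 1/200) = 2.80, and power = Φ(2.80 − 1.96) = 80%. This reproduces. The plan states no figure for the usage analysis.

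**2. Spurious dose effect within one arm.** Usage is set by cutting a latent normal variable that correlates r with change. Write m(p) = φ(z_p)/p for the mean of that variable in a tail of proportion p, where z_p is the normal cut point. Then all − none = r × [m(p_all) + m(p_none)], with standard error √(1/(200·p_all) + 1/(200·p_none)).

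The values are m(.10) = 1.755, m(.20) = 1.400, m(.50) = .798 and m(.60) = .644.

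| none / all | bracket | r = .1 | r = .2 | r = .3 |
|---|---|---|---|---|
| 10% / 50% | 2.553 | .26 SD, 18% | .51 SD, 55% | .77 SD, 88% |
| 10% / 60% | 2.399 | .24 SD, 17% | .48 SD, 51% | .72 SD, 85% |
| 20% / 50% | 2.198 | .22 SD, 22% | .44 SD, 65% | .66 SD, 94% |
| 20% / 60% | 2.044 | .20 SD, 20% | .41 SD, 61% | .61 SD, 92% |

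The percentages are the chance of p < .05. Example: r = .3, none 15%, all 55% gives .3 × (1.554 + .720) = .68 SD; standard error √(1/30 + 1/110) = .206; z = 3.31; chance 91%. From r = .2 the spurious difference exceeds .28.

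If half of the no-session group lacks follow-up (a further assumption), the SD differences stay the same and the chances fall to about 11-15%/31-43%/59-77%.

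**3. Facilitated versus self-guided among finishers.** Bias = r × [m(p_self) − m(p_fac)]. With 70-80% finishing in facilitated (m = .497 to .350) and 30-50% in self-guided (m = 1.159 to .798):

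- Smallest gap, 70% v 50%: .301r = .03/.06/.09 SD, with false positives of about 6%/8%/11%.
- Largest gap, 80% v 30%: .809r = .08/.16/.24 SD, with false positives of about 8%/19%/36%.

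With equal completion and the same selection in both arms the two terms cancel and the bias is zero.

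**4. Check by simulation.** 4,000 null trials per scenario were run, using one change score instead of the full mixed model. Completion (none/some/all) was 20/30/50 in both arms, or 15/25/60 v 25/35/40, or 10/20/70 v 30/40/30.

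- Arms as randomized, ignoring usage: 4.5-5.5% false positives in every scenario.
- Change by usage within an arm: about 5% at r = 0, then 15-18%/50-62%/88-95% at r = .1/.2/.3.
- Arm effect adjusted for usage: 5.2%/4.4%/4.7% with equal completion, 6.5%/10.7%/18.6% with the modest gap, 10.2%/26.9%/53.1% with the large gap.
- Finishers only, large gap: 7.0%/13.8%/26.6%.

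**The case against.** The strongest reply is about scope. Usage is a supplementary paragraph. The preceding SAP model compares Facilitated, Self-Guided and Control as randomized, without usage, and no passage says that usage results will decide delivery mode or number of sessions. That stands: a reader might infer that the trial's delivery-mode conclusion is compromised, and the documents do not support it.

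A reader might also infer that the SAP will test the arms against each other within each usage level. It does not say so, and it lists no interaction terms. The reading is plausible, because an arm term fitted beside usage is conditional on usage, but it is not stated text.

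Nor do the documents show that self-guided would look better. That sign follows from assuming the same positive correlation in both arms. Because the outcome is change, stable differences in level largely cancel. Distressed caregivers might complete less yet have more room to improve. The finisher bias also stays below .28 SD throughout the assumed range.

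The significance rates in step 2 assume full follow-up. Nothing is collected after withdrawal (sections 11.0 and 15.0), and non-starters may be the likeliest to withdraw, so the rates may be too high.

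Finally, the absence of usage from the Aim 3 moderators (age, gender, baseline stress) is weak evidence of a departure. The protocol has no full analysis section and did plan to collect adherence data.

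None of this removes the central point: a post-randomization variable is called a moderator and tested at 0.05 with no allowance for selection.

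**Conclusion.** The point holds for the usage paragraph and goes no further. A false dose effect needs only a common cause of completion and change. Under the assumed ranges it is about .20-.26/.41-.51/.61-.77 SD at r = .1/.2/.3, significant in about 17-22%/51-65%/85-94% of trials with complete follow-up and less often without it.

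A false delivery-mode difference needs more: completion rates, or the type of person who completes, must differ between arms. It is then about .03-.08/.06-.16/.09-.24 SD among finishers, with 6-8%/8-19%/11-36% false positives and unknown direction. It vanishes when completion and selection are equal.

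These are ranges under stated assumptions and do not predict this trial's result. The comparison of arms as randomized keeps its error rate.

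**What to change.** In the SAP's usage paragraph:

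1. Replace the clause "to assess how the number of weeks completed moderate the effect of intervention on change in each outcome" with wording that reports change in each LEAF arm by none, some or all sessions as a descriptive association that does not support a causal reading.
2. Make no significance claim for a dose effect, or for facilitated versus self-guided conditional on usage.
3. State that delivery-mode conclusions come only from the comparison of arms as randomized.

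The SAP is dated 10/20/2025 and written in the past tense, so the analyses appear to be done. The change is to wording and reporting and costs almost nothing.

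Optional sensitivity analysis: for each LEAF arm against control up to FU2 (which appears to be T4, before crossover), estimate the complier-average effect of starting LEAF, meaning at least one session. State the exclusion assumption that assignment has no effect on those who never start. The protocol (section 8.0, waitlist control) gives it partial support: "Note that participants in the LEAF intervention conditions will also be completing the daily reporting of emotions and stress". It remains open to debate, because LEAF arms also have home practice and skills review, self-guided users have discussion and awards features, and tablets arrive earlier than for controls. The data are already collected; the price is wider intervals and an untestable assumption. A per-session instrumental-variable estimate is not needed: with assignment as the only instrument it is the randomized difference divided by mean sessions, and it cannot separate none, some and all.
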